4.2.4 Follow-up phase

Patients who discontinue study treatment will continue to have response assessments performed every 12 weeks until documented relapse, and thereafter will be followed every 3 months for survival except those who are lost to follow-up. Data on anti-neoplastic therapies will be collected as well.

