7.1 Study flow and visit schedule

Table 7-1 lists all of the assessments and indicates with an “X”, the visits when they are performed. All data obtained from these assessments must be supported in the patient’s source documentation.

The table indicates which assessments produce data to be entered into the clinical database (D) or remain in source documents only (S) (“Category” column). No CRF will be used as a source document.

Allowed visit windows are specified as follows:

- Screening assessments listed below, must occur within 14 days prior to Day 1 as per Table 7-1.
- During each induction and consolidation cycle, PK and ECG assessments must be performed on the specified day. Local measurements of $QTc \geq 480ms$ will be centrally verified on a copy of a high quality recording that includes time and voltage scales.
- All other assessments should not exceed a 5 day window to take into account scheduling over public holidays if not explicitly specified otherwise.

Every effort should be made to follow the schedule outlined in Table 7-1.

[figure not shown]
[figure not shown]

[figure not shown]
Table 7-1 Visit evaluation schedule

A: Screening until end of consolidation phase

[figure not shown]
	Category	Protocol Section	Screening Phase	Induction Phase Cycle 1-2														End of Induction Phase / EOT	Prior to each cycle of Consolidation phase	Consolidation Phase/HSCT Cycle 1-4														End of Consolidation Phase / EOT
Visit name	D		S C R	INDUCTION C1-C2														IND DISPO SITION		CONSOLIDATION C1- C4														CON DISPO SITION
Day of cycle			-14 to -1	1	2	3	4	5	7	8	11	15	18	21	24	27	28		1	2	3	4	8	11	15	17	21	27	28					
Informed consent																																		
Obtain study Informed Consent	D		x																															
IRI																																		
Registration	D		x																															
Randomization: I1, D8: when FLT3 mutation status is confirmed	D									x I1																								

[figure not shown]
	Category	Protocol Section	Screening Phase	Induction Phase Cycle 1 -2	End of Induction Phase / EOT	Prior to each cycle of Consolidation phase	Consolidation Phase/HSCT Cycle 1-4	End of Consolidation Phase / EOT	
Visit name	D		S C R	INDUCTION C1-C2	IND DISPO SITION		CONSOLIDATION C1- C4	CON DISPO SITION	
Day of cycle			-14 to -1	1 2 3 4 5 7 8 11 15 18 21 24 27 28			1 2 3 4 8 11 15 17 21 27 28		
Prior antineoplastic medications	D		x						

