E Treatment discontinuation due to lack of efficacy without documented relapse in the consolidation and post-consolidation treatment phases.	Date of last adequate response assessment	Censored

Of note, a response assessment (especially relapse) can also be done based on one component of response, e.g. peripheral blood.

Missing adequate response assessment is defined as an assessment not done or classified as ‘unknown’. For simplicity, the ‘missing adequate response assessment’ will also be referred as ‘missing assessment’.

As detailed in [Table 7-1](#), the EFS censoring and event date options depend on the presence and the number of missing assessments.

An exact rule to determine whether there are any missing assessments is needed after end of the induction phase. This rule will be based on the distance between the last adequate response assessment date and the event date.

The threshold D1 is defined as the interval between the response assessments plus the protocol-allowed window around the assessments. Similarly, the threshold D2 is defined as 2 times the protocol-specified interval between the response assessments plus the protocol allowed window around the assessments.

During consolidation and post-consolidation treatment phases:

Response assessment are performed **between day 21 and day 28** of each cycle:

- Therefore, for patients with a previous CR or CRi with adequate blood count recovery, the next assessment will be done on the next cycle between day 21 and day 28. The threshold D1 is defined as 28 days (maximum cycle length for patient with CR or CRi

with adequate blood count recovery) + 7 (in case the last assessment was done on day 21) = 35 days and the threshold D2 as 70 days.

- For patients with a previous CRi without adequate blood count recovery, the cycle will be prolonged up to 21 days. Therefore, the threshold D1 is defined as 7 (in case the last assessment was done on day 21) + 21 = 28 days and the threshold D2 is 56 days.

During follow-up phase:

- The threshold D1 is defined as 90 days and the threshold D2 as 2 * 90 days = 180 days

The analysis will assume one missing assessments if the distance between the last adequate response assessment and the event date is within (D1, D2] and 2 or more missing assessment if the distance is larger than D2.

EFS will be summarized between the 2 treatment groups within each of the following subgroups as defined in section 3.8.5. by forest plots

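### The follow-up EFS threshold D2 of 180 days omits the visit window, so on a 3-monthly schedule a relapse found on its nominal date after one missed visit is censored

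*SAP*

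**What the plan says.** SAP 7.2.1 gives a general definition. For the first threshold: "The threshold D1 is defined as the interval between the response assessments plus the protocol-allowed window around the assessments". For the second: "the threshold D2 is defined as 2 times the protocol-specified interval between the response assessments plus the protocol allowed window around the assessments". It then fixes numbers for each phase. For follow-up: "The threshold D1 is defined as 90 days and the threshold D2 as" twice 90, that is 180 days. On treatment, for patients in CR or CRi with adequate recovery, D1 is 28 + 7 = 35 days and D2 is 70. For CRi without recovery the pair is 28 and 56.

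A gap above D1 and up to D2 counts as one missed assessment. The SAP assumes "2 or more missing assessment if the distance is larger than D2". In SAP Table 7-1, row B2 counts a relapse after exactly one missed assessment as an event on its own date. Row B3 censors a relapse after two or more at the last adequate assessment. Protocol 10.4.2 states the same two rules in words.

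On the schedule, the protocol synopsis and part B of the visit evaluation schedule (protocol Table 7-1) have follow-up response assessed every three months, while protocol 4.2.4 has "response assessments performed every 12 weeks until documented relapse". For the window, protocol 7.1 says "All other assessments should not exceed a 5 day window to take into account scheduling over public holidays", and protocol 7.1.3 gives it as plus or minus 5 days.

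**The concern.** The D1 and D2 constants are meant to put rows B2 and B3 into effect. In follow-up the constant departs from its own definition, and on a 3-monthly schedule it gives the opposite result from the rule it implements. A patient who misses one visit and attends the next on its due date is handled as if two had been missed. The relapse leaves the primary endpoint, and the patient is censored about six months earlier.

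What is at stake is the accuracy of the EFS hazard ratio, its confidence interval, the Kaplan-Meier curve and the subgroup forest plots in the final report. There is also a mismatch within that report. The SAP's document history says DFS and CIR now count all events regardless of missed assessments, so the same relapse can be an event for DFS and censored for EFS.

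**Working it through.** **Inputs.** Interval I: 3 months (protocol synopsis and visit schedule), 84 days (12 weeks, protocol 4.2.4), or the 90 days used in the SAP. Window w: 5 days either side (protocol 7.1 and 7.1.3). Definition: D1 = I + w and D2 = 2I + w.

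**1. Reproducing the SAP figure.** With I = 90 and w = 0, D1 = 90 and D2 = 180. With w = 5, D1 = 95 and D2 = 2×90 + 5 = 185, or 2×(90 + 5) = 190 if the window is doubled too. With I = 84 and w = 5, D1 = 89 and D2 = 173 (178 doubled). Among these, 90/180 appears only when the window is zero.

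**2. Relapse on the nominal date.** Counting six calendar months from each of 2,922 start dates (mid-2018 to mid-2026) gives 181 days (732 dates), 182 (612), 183 (624) or 184 (954). All exceed 180, so row B3 applies in every case.

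**3. Relapse elsewhere in the window.** Assume each day from −5 to +5 is equally likely. At 90-day spacing with the last visit on its date, the gap runs from 175 to 185 days, and 5 of 11 days (181 to 185) exceed 180: 45%. On calendar months the shares are 6/11, 7/11, 8/11 and 9/11 for nominal gaps of 181 to 184. Weighted by the counts above, that is 22,254/32,142 = 69%, or 67% when the last visit also varies.

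| Spacing | Gap after one missed visit, both visits in window | Share above 180 days | Smallest D2 covering all |
|---|---|---|---|
| 12 weeks | 2×84 ± 10 = 158 to 178 | 0% | 178 |
| 90 days | 2×90 ± 10 = 170 to 190 | 45% | 190 |
| Calendar months | 181 − 10 to 184 + 10 = 171 to 194 | 67% to 69% | 194 |

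**4. Is 185 enough?** No. It still leaves 24% to 28% above the threshold on calendar months, and 0% to 12% at 90-day spacing.

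**5. Would a larger D2 admit real double misses?** The shortest in-window gap after two missed visits is 3×90 − 10 = 260 days at 90-day spacing. Both 190 and 194 are far below it.

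**6. D1.** Its shortfall changes nothing, because no missed assessment and one missed assessment both lead to an event.

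**7. On treatment.** Read literally, D2 = 2×28 + 7 = 63. The stated 70 is 2×(28 + 7). With 28-day cycles the longest gap after one miss runs from day 21 to day 28 two cycles later, 2×28 + 7 = 63, which 70 covers. Protocol 6.1.5 allows consolidation cycles of up to 50 days. Two such cycles could give 2×50 + 7 = 107, above 70, if no adequate assessment is recorded in between.

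**The case against.** The strongest reply is that the consequence depends on the interval. If the 12-week interval applies, the longest in-window gap after one miss is 178 days and nothing is lost. On exact 90-day spacing, day 180 itself still counts because the range includes its upper limit. Both points stand. A reader might infer that every relapse after one missed visit is censored; the documents do not support that, since any visit at or before day 180 is counted. Relapse can also be assessed at any time on suspicion, so many relapses will not fall on a scheduled date.

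Second, the on-treatment difference between 63 and 70 can be called a matter of parsing, since the SAP doubles D1 in every phase (35/70, 28/56, 90/180) and states 70 outright. That also stands. Lowering D2 to 63 would censor relapses at days 64 to 70 that now count. However, the doubling reading does not rescue follow-up, where it would give 190.

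Third, cycles are prolonged for patients in CRi without adequate recovery, who have their own thresholds and are reassessed during the extension. This makes a 107-day gap an outer limit, but does not remove the problem when a reassessment is missing.

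Fourth, censoring after two or more missed assessments is itself specified in the protocol. Whether that rule is informative is a separate question from whether the constant implements it.

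**Conclusion.** The follow-up constant is wrong as written: D2 = 180 does not follow from the SAP's definition. On a calendar 3-monthly schedule it reverses row B2 for any relapse found on its nominal date after one missed visit. This rests on the three-month reading of the interval and a window of plus or minus 5 days. The 67% to 69% and 45% shares also assume that visit days are uniform within the window.

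The number of patients affected cannot be derived. Neither document gives the number of relapses in follow-up or the rate of missed visits, so any count of lost events would be a guess. A reader might also infer that the trial's conclusion is at risk. The documents do not show that: the study had stopped for futility, and SAP section 7 reports EFS without p-values. What is affected is the descriptive EFS output.

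**What to change.** 1. Reconcile the follow-up response interval between protocol 4.2.4 (12 weeks) and the synopsis and visit schedule (3 months), and state the one used in SAP 7.2.1.
2. Set follow-up D2 to allow the window at both visits: 190 days at 90-day spacing, or 194 on calendar months. If the interval is 12 weeks, 178 is enough and the present 180 already covers it. State D1 on the same basis for consistency.
3. On treatment, keep D2 = 70 and reword the definition as twice the sum of interval and window. Do not reduce it to 63.
4. Where consolidation cycles are prolonged, count missed assessments from actual cycle and visit dates instead of a fixed day count.
5. Because the SAP was revised after unblinding, record the derivation with the change and list the patients whose EFS status it alters.

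The cost is a short SAP edit, one constant and a modest change to the EFS program. No new data are needed.

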8.1 Key secondary endpoint - overall survival (OS)

OS is defined as the time from date of randomization to date of death due to any cause. If a patient is not known to have died, survival will be censored at the date of last contact.

Table 8-1 Primary OS analysis (event date / outcome)

Situation	Options for event date	Outcome
A Death	Death date	Event
B Death after New anticancer therapy / HSCT	Death date	Event
C Withdrawal of consent	Last contact date prior to withdrawal of consent	Censored
D No death	Last contact date	Censored

8.2 Statistical hypothesis, model, and method of analysis

Assuming proportional hazards model for OS, the following statistical hypothesis for OS will be tested using a stratified log-rank test (stratified according to randomization stratification factor of age) at the one-sided 2.5% level of significance:

$$H02: \theta2 \geq 1 \text{ vs. } Ha2: \theta2 < 1$$

Where $\theta2$ is the hazard ratio (Midostaurin treatment arm vs. placebo arm) of OS.

The analyses for OS will be based on the FAS population according to the treatment group patients were randomized and the strata they were assigned at randomization. For the final CSR, OS will be summarized only descriptively. No testing will be performed. For the original testing plan, please refer to study protocol. OS will be estimated using the Kaplan-Meier method. The median OS along with 95% confidence intervals will be presented by treatment group. The stratified Cox regression will be used to estimate the HR of OS, along with 95% confidence interval. All OS analyses will be based on the FAS.

OS will be summarized between the 2 treatment groups within each of the subgroups as defined in [Section 3.8.5](#).

HRs and 2-sided 95% CIs will be provided based on the stratified Cox proportional hazards model. This model will use the BY statement to derive estimates by subgroup. Point estimates of HR and 2-sided 95% CI will be provided by subgroup in a forest plot.

8.3 Analysis of secondary endpoints

The secondary efficacy variables include CR or CRi with adequate blood count recovery rate, MRD, DFS, CIR and CID. The assessment of these endpoints, except MRD, will be based on the IWG criteria for AML [[Cheson et al 2003](#), [ELN 2017 / Döhner et al 2017](#)] as per investigator assessment. All these endpoints will only be descriptively summarized with 95% CIs but without any p-values.

The rate of CR/CRi with adequate blood count recovery will be analyzed based on the FAS. However, DFS, Cumulative Incidence of Relapse (CIR) and Cumulative Incidence of Death (CID) will be analyzed based on data from responders (CR or CRi with adequate blood count recovery within 93 days after start of treatment) in the FAS. Assessment of relapse from CR or CRi with adequate blood count recovery, DFS, CIR and CID will not consider whether a patient received HSCT. All secondary analyses will include all data observed up-to the cut-off date, unless otherwise specified.

8.3.1 CR/CRi rate

Number and percentage of patients achieving CR or CRi with adequate blood count recovery rate will be reported by cycle of induction therapy (i.e. cycle 1 or cycle 2) and by treatment phases. Patients with CR /CRi with adequate blood count recovery after 93 days after start of chemotherapy are considered as induction failure and thus will not be reported as responders. Those patients will be listed separately.

Response assessment as per investigator evaluation will be listed for all patients by treatment group. Bone marrow, platelet, neutrophils, auer rods, extramedullary disease and transfusion assessment will be listed as well.

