10.5.2 Other secondary efficacy objectives

10.5.2.1 CR/CRi rate, Time to CR or CRi with adequate blood count recovery, Disease Free survival (DFS), Cumulative Incidence of Relapse (CIR) and Cumulative Incidence of Death (CID)

Other secondary efficacy variables include CR or CRi with adequate blood count recovery rate, DFS, CIR and CID. The assessment of these endpoints will be based on the IWG criteria for AML ([Cheson et al 2003](#), [ELN 2017 / Döhner et al 2017](#)) as per investigator assessment.

CR/CRi with adequate blood count recovery rate will be analyzed using Cochran-Mantel-Haenszel test based on strata at randomization. Estimated CR/CRi rate along with corresponding 95% confidence intervals will be presented by stratum and overall, and by treatment group.

Time to CR or CRi with adequate blood count recovery is defined as the time from randomization to CR or CRi with adequate blood count recovery whichever occurs first. Patients without experiencing CR, CRi with adequate blood count recovery will be censored according to the following events:

- Patients experiencing induction failure will be censored at maximum follow-up (i.e. date of FPFV to date of LPLV used for the analysis).
- Patients not experiencing induction failure and who did not die (any cause) will be censored at their last adequate response assessment date which is different from “unknown” or “not done”.

DFS is defined as the time from CR or CRi with adequate blood count recovery to relapse or death due to any cause. Patient who did not relapse nor die will be censored at the last adequate response assessment.

DFS will be estimated using the Kaplan-Meier method. The median DFS along with 95% confidence intervals will be presented by treatment group. The stratified Cox regression will be used to estimate the HR of DFS, along with 95% confidence interval.

Cumulative Incidence of Relapse (CIR) is defined for patients with CR or CRi with adequate blood count recovery and is time from achieving the CR or CRi with adequate blood count recovery until the onset of relapse from CR or CRi with adequate blood recovery. Patients without relapse are censored at the last adequate response assessment. Patients who died without relapse are counted as a competing cause of failure.

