This statistical analysis plan (SAP) describes all planned analyses for the clinical study report (CSR) of study CPKC412E2301: a phase III, randomized, double-blind clinical trial of chemotherapy with daunorubicin or idarubicin and cytarabine for induction and intermediate dose cytarabine for consolidation plus midostaurin (PKC412) or placebo in newly diagnosed patients with FLT3-MN (SR<0.05) AML (FLT3 mutant to wild type signal ratio below the 0.05 clinical cut-off).

The content of this SAP is based on protocol CPKC412E2301 amendment 1. All decisions regarding final analysis, have been made prior to final database lock but after unblinding of the study data.

The first interim analysis of the primary endpoint (Event Free Survival (EFS)) for futility has been performed and the study was stopped due to lack of efficacy on 23-Sep-2019 based on DMC recommendation. Subsequently, investigators were notified on the futility outcome and study was unblinded not only for Novartis but also the investigators. While majority of patients discontinued from the study within subsequent weeks, some patients decided to continue protocol planned study treatment. This SAP now describes the analyses for the final CSR which will be generated when all patients discontinued study treatment.

The originally planned efficacy and safety analyses are reduced based on the futility outcome. However, some subgroup analyses have been added (e.g. safety and efficacy by anthracyclin for AML induction therapy (Daunorubicin vs Idarubicin)) and some analyses are only performed now for the final CSR (e.g. QoL, PK, [REDACTED]).

2 Study design, objectives and endpoints

[figure not shown]
This is a randomized, double-blind, multi-center, placebo-controlled phase III study using a group sequential design with two interim analyses for the primary endpoint event-free survival (EFS) and regular safety looks. The study population comprises 502 adult patients with newly diagnosed FLT3-MN (SR<0.05) AML. Patients will be stratified according to age (<60 vs. ≥ 60 years) and will be randomized in a 1:1 ratio into one of two treatment arms:

- Midostaurin + chemotherapy

Or

- Placebo + chemotherapy

Figure 2-1 Study design

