Other **secondary** [REDACTED] **objectives** are:

Objective	Endpoint
To compare CR + CRi with adequate blood count recovery rate in the two treatment groups.	CR and CRi with adequate blood count recovery rate according to the International Working Group (IWG) for AML [Cheson et al 2003, ELN 2017 / Döhner et al 2017] as per investigator assessment.
To compare the percentage of patients who reached CR or CRi with adequate blood count recovery with MRD negative bone marrow in the two treatment groups.	Percentage of patients with CR or CRi with adequate blood count recovery with MRD negative bone marrow.
To compare the time to MRD- between the two treatment arms in the two treatment groups.	Number of days from date of randomization to first documented MRD-
To compare the percentage of patients with MRD negative status in the post-consolidation phase in the two treatment groups.	Percentage of patients with MRD negative status during post-consolidation Phase
To compare DFS, as well as the Cumulative Incidence of Relapse (CIR) and Cumulative Incidence of Death (CID) in the two treatment groups.	
DFS, as measured from the date of first CR or CRi with adequate blood count recovery to relapse or death from any cause, whichever occurs first.
 
CIR is defined for patients with CR or CRi with adequate blood count recovery: time from achieving CR or CRi with adequate blood count recovery until onset of relapse. Patients without relapse are censored at the last adequate response assessment. Patients who died without relapse are counted as a competing cause of failure.
 
CID is defined for patients with CR or CRi with adequate blood count recovery: time from achieving CR or CRi with adequate blood count recovery until death. Patients who did not die are censored at the last contact date. Patients who relapsed are counted as a competing cause of failure.

To compare the time to CR or CRi with adequate blood count recovery in the two treatment groups.	Number of days from date of randomization to first documented CR or CRi with adequate blood count recovery.
To compare the time to neutrophil recovery in the two treatment groups.	
Number of days from the first day of a chemotherapy cycle to first day neutrophils $\geq 0.5 \times 10^9/L$.
 
Number of days from day 1 of commencing induction therapy to first day neutrophils $\geq 1.0 \times 10^9/L$.

Objective	Endpoint

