6.8 Dose reductions, interruptions or permanent discontinuations

‘Dose changed’, ‘Dose interrupted’, and ‘Dose permanently discontinued’ fields from the exposure eCRF pages will be used to determine the dose reductions, dose interruptions, and permanent discontinuations, respectively.

The corresponding fields ‘Reason for dose change/dose interrupted’ and ‘Reason for permanent discontinuation’ will be used to summarize the reasons.

A dose change is either ‘change in prescribed dose level’ or ‘dosing error’ where actual dose administered is different from the prescribed dose.

For the purpose of summarizing interruptions and reasons, in case multiple entries for interruption that are entered on consecutive days with different reasons will be counted as separate interruptions. However, if the reason is the same in this block of entries, then it will be counted as one interruption.

Reduction: A dose reduction is, where the prescribed dose level is lower than the previous prescribed dose level or where the actual dose administered is lower than the calculated dose amount based on the prescribed dose. Therefore any dose change to correct a dosing error will not be considered a dose reduction. Only dose change is collected in the CRF, number of reductions will be derived programmatically based on the change and the direction of the change. In addition, if a patient moves to a less frequent regimen, such changes will then be counted as dose reductions.

7 Analysis of the primary objective

The primary objective of this study was to determine if the addition of midostaurin to standard induction and consolidation therapy, followed by single agent post-consolidation therapy improves event-free survival (EFS) in patients with newly diagnosed FLT3-WT AML.

As the study concluded at the first efficacy interim analysis due to futility, the endpoints will be derived and summarized based on the final data, but no testing (p-values) will be provided in the final CSR.

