9.13.2 Second EFS interim analysis

Since the study was stopped at first interim analysis, no further analyses were performed.

10 Sample size calculation

The assumption of median EFS of 12.0 months for the control treatment arm for sample size calculations is based on available data for patients with FLT-MN (Bacher et al 2008). It is expected that treatment with test treatment arm will result in a 37.5% reduction in the hazard rate (corresponding to an increase in median EFS from 12.0 months to 17.8 months under the exponential model assumption).

If the true hazard ratio is 0.675, a total of 285 EFS events are required to have 90% power at an one-sided overall 2.5% level of significance to reject the null hypothesis ($HR \geq 1$) using a log-rank test and a 2-look group sequential design with Haybittle-Peto boundary to determine efficacy boundary and gamma spending function ($\gamma = -1.2$) to determine the non-binding futility boundary. Considering a recruitment period of approximately 20 months assuming an increasing recruitment rate to reach 30 patients / month in month 6, 502 patients will need to be randomized to the two treatment arms in a 1:1 ratio. Assuming about approximately 10% patients will be lost to follow-up for EFS, a total of 502 patients will need to be randomized. Given the above assumptions, it is estimated that the 285th EFS event will be observed at approximately 40 months from the date of first patient randomized in the study. The sample size calculation was conducted with software package [East 6.4].

11 Change to protocol specified analyses

No change from protocol specified analysis was made. [REDACTED]

12 Appendices

Please refer to original SAP.

13 Reference

[Allison PD (2000)] Survival analysis Using the SAS system. Cary, NC, SAS Institute Inc.

[Brookmeyer R. and Crowley J. (1982)] A Confidence Interval for the Median Survival Time, *Biometrics* 38, 29-41

[Collet D (1994)] Modelling survival data in medical research. London, Chapman & Hall

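### The SAP drops the protocol's age-stratified comparison of the CR/CRi rate without putting a between-arm estimate in its place, and SAP Section 11 says that nothing changed

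*SAP*

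**What the plan says.** Protocol 10.5.2.1 sets the method for the response rate: "CR/CRi with adequate blood count recovery rate will be analyzed using Cochran-Mantel-Haenszel test based on strata at randomization". It adds how the rates are to be shown: "Estimated CR/CRi rate along with corresponding 95% confidence intervals will be presented by stratum and overall, and by treatment group". It names no risk difference or odds ratio.

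The objectives table in SAP Section 2 keeps the comparative aim: "To compare CR + CRi with adequate blood count recovery rate in the two treatment groups". The analysis text in SAP 8.3.1 is descriptive: "Number and percentage of patients achieving CR or CRi with adequate blood count recovery rate will be reported by cycle of induction therapy", and also by treatment phase. SAP 8.3 sets the general rule for the secondary endpoints: "All these endpoints will only be descriptively summarized with 95% CIs but without any p-values".

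The reason for reducing the analyses is given openly. The SAP Introduction says: "The originally planned efficacy and safety analyses are reduced based on the futility outcome". The opening of SAP Section 7 says: "the endpoints will be derived and summarized based on the final data, but no testing (p-values) will be provided in the final CSR". The Introduction also says that decisions on the final analysis were taken before database lock but after unblinding, and that some subgroup analyses were added.

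SAP Section 11, which exists to record departures from the protocol, reads: "No change from protocol specified analysis was made". The text after that sentence is redacted.

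**The concern.** Two things are at stake.

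First, the CR/CRi rate is the response component of the primary endpoint, since failing to reach CR or CRi with adequate count recovery in induction is itself an EFS event. A reader of the report will want to know by how much the arms differ in response and how precisely that is known. Separate percentages with separate intervals do not say so directly.

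Second, Section 11 is where a reader of the report looks for departures from the protocol. If its sentence is carried forward, the report will deny changes that the same SAP describes elsewhere, some of them decided with treatment codes known.

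**Working it through.** **Step 1: the CR/CRi rate in the two documents.**

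| Item | Protocol 10.5.2.1 | SAP 2, 3.8.5, 8.3, 8.3.1 |
|---|---|---|
| Aim | Compare arms | Compare arms |
| Between-arm method | CMH test on randomization strata | None named |
| Effect measure | None named | None named |
| Rates with 95% CI | By stratum, overall, by arm | By arm, induction cycle and phase |
| Age display | Randomization strata | Subgroup summary by age derived from baseline data |
| p-value | Yes, from the test | Ruled out |

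What was lost is the only between-arm analysis of this endpoint. SAP 3.8.5 says that the subgroup summaries, CR/CRi included, are meant to examine the treatment effect, but its forest plots cover only EFS, OS, DFS, CIR and CID.

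**Step 2: the SAP's handling of other comparative objectives.**

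- OS (SAP 8.2): stratified Cox hazard ratio with 95% CI, no test.
- DFS, CIR, CID (SAP 8.3.3 to 8.3.5): stratified Cox hazard ratio with 95% CI, no p-value.
- Neutrophil and platelet recovery (SAP 8.3.7): hazard ratio with 95% CI, where protocol 10.5.2.3 planned medians only.
- MRD-negative rate (protocol 10.5.2.2, SAP 8.3.6.1): per-arm percentage with exact 95% CI in both documents.

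An effect estimate with an interval and no p-value is therefore the SAP's own convention after the stop. CR/CRi is the endpoint that had a protocol comparison, lost it, and received no estimate.

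**Step 3: Section 11 against the rest.** These protocol analyses have no counterpart in the SAP text:

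- the CMH test (protocol 10.5.2.1);
- the per-protocol set (protocol 10.1.3; SAP 3.8 defines only the full analysis, safety and PK sets);
- the EFS sensitivity analyses (protocol 10.4.3);
- the Cox model for EFS adjusting for transplant, MRD and other prognostic factors (protocol 10.4.3).

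SAP 3.8.5 also lists subgroups that the protocol does not name: anthracycline, ITD/TKD signal ratio and region. The Introduction gives anthracycline as an example of an addition. The visible Section 11 sentence cannot be reconciled with these differences.

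**Step 4: size, as illustration only.** The plan gives no sample size, power or expected rate for CR/CRi, so there is no figure of its own to reproduce. Assume the same true rate p in both arms and n patients per arm. The largest n is the planned 502/2 = 251; 100 and 150 are assumed.

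- Per-arm half-width: 1.96 × √(p(1−p)/n).
- Difference half-width: 1.96 × √(2p(1−p)/n).
- Example, p = 0.5 and n = 150: 1.96 × √(0.5/150) = 0.113, or 11.3 points.

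| n per arm | Per-arm half-width, p = 80% to 50% | Difference half-width, p = 80% to 50% |
|---|---|---|
| 100 | 7.8 to 9.8 points | 11.1 to 13.9 points |
| 150 | 6.4 to 8.0 points | 9.1 to 11.3 points |
| 251 | 4.9 to 6.2 points | 7.0 to 8.7 points |

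Per-arm intervals are not a substitute for the interval on the difference. With equal standard errors, two 95% intervals that just fail to overlap are 2 × 1.96 standard errors apart. The difference has √2 times that standard error, so z = 2 × 1.96/√2 = 2.77 and two-sided p = 0.0056.

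**Step 5: what stratification adds.** Assume 175 per arm, half of each arm in each age group, and rates of 70% below age 60 and 45% above, so 57.5% overall.

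- Unstratified: 1.96 × √(2 × 0.575 × 0.425/175) = 10.4 points.
- Stratified: mean within-stratum variance (0.21 + 0.2475)/2 = 0.22875, so 1.96 × √(2 × 0.22875/175) = 10.0 points.

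The gain in precision is small. The reason to stratify is agreement with the randomization and the protocol.

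**The case against.** The strongest reply is that the trial stopped for futility, that removing tests was deliberate, and that the SAP says so in its Introduction, in Section 7 and in 8.3. The history table ties the second version to the futility outcome and marks all sections as affected. The protocol's CR/CRi entry is a test with no named effect measure, so a risk difference would not literally restore it. Any reader can compute an unstratified difference from the per-arm counts, and summaries by age remain under SAP 3.8.5.

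Most of this stands. Dropping the p-value needs no defence, and the disclosure elsewhere makes it unlikely that a careful reader of the whole SAP would be misled. It does not explain why response alone loses its comparison while the time-to-event endpoints keep theirs, and it makes Section 11 harder to reconcile with the rest.

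Several stronger readings are tempting but are not supported:

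- A reader might infer that the SAP's comparative objectives in general get no treatment effect. OS, DFS, CIR, CID and count recovery do.
- A reader might infer that a stratified MRD comparison was also removed. The protocol never had one for the MRD-negative rate.
- A reader might list the restriction of DFS, CIR and CID to responders within 93 days as an undisclosed change. Protocol 10.5.2.1 already limits these endpoints to responders, and protocol 4.2 already classes patients without response by day 93 as induction failures.
- A reader might infer that sizeable differences would go unseen because the arms' intervals overlap. The SAP states no overlap rule, and the inputs to such a calculation are not in the documents.
- A reader might treat every departure as decided after unblinding. The first SAP version is dated 02-Sep-2019, before the stop on 23-Sep-2019, and is not among the documents, so most items cannot be dated individually. The protocol's subgroup lists are also open-ended.

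**Conclusion.** The point holds for the CR/CRi rate and for Section 11, and no further. The SAP removes the protocol's only between-arm analysis of this endpoint and names no replacement, although the objective remains comparative and its own practice elsewhere is to give an estimate and interval without a test. The visible Section 11 sentence is wrong as written; the redacted text after it may add detail, but it could not make an unqualified denial of change agree with the Introduction.

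The consequence is modest: a gap in the reporting of one secondary endpoint and an inaccurate record of changes. It does not touch the futility decision. The precision range of 7.0 to 13.9 points rests entirely on assumed rates and arm sizes and shows only what the missing interval would look like.

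**What to change.** **SAP 8.3.1.** Add: the difference in CR/CRi rate (midostaurin minus placebo) in the full analysis set will be estimated as the Mantel-Haenszel risk difference, stratified by age group as recorded in the IRT, with a 95% confidence interval and no p-value. Keep the per-arm rates with intervals, and show them by IRT stratum as well as overall, as the protocol planned. Using the IRT stratum follows SAP 3.8.4 for stratified analyses.

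**SAP 8.3.6.1 (optional).** The same estimate could be given for the MRD-negative rate. Label it as an addition to the protocol.

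**SAP Section 11.** Replace the sentence with a list of:

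- dropped analyses: the CMH test for CR/CRi, the per-protocol set, the EFS sensitivity analyses and the covariate-adjusted Cox model for EFS;
- subgroups that the protocol does not name, such as anthracycline, signal ratio and region;
- for each item, whether it was decided before or after unblinding. The sponsor can date these from the first SAP version. Those decided after unblinding should be marked post hoc in the report.

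The cost is one extra column in the response table, its by-stratum rows and one rewritten paragraph. No new data are needed.
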